DilaCheck® Trial

TITLE:

**Inter-examiner Agreement of a Novel Device for the Measurement of Cervical
Dilation in Labor: A Randomized Controlled Trial**

NCT Number: 03440723

Date of the Document: January 1, 2019

PROTOCOL

TITLE: Inter-examiner Agreement of a Novel Device for the Measurement of Cervical Dilatation in Labor: A Randomized Controlled Trial

ABBREVIATED TITLE: DilaCheck® Trial

PROTOCOL SUMMARY

Measurement of cervical dilation during late pregnancy and labor informs decisions in the management of labor and delivery. Prior published research suggests that practitioners are only 48 to 56% accurate when judging cervical simulators.¹⁻³ When measuring laboring women, two practitioners' measurements agree only 49% of the time.⁴ [name] of Elm Tree Medical Inc. (the Sponsor) developed a novel device, DilaCheck®, to enable practitioners to increase accuracy in cervical dilation measurements.

Elm Tree Medical completed a preliminary trial using a simulator similar to those used in prior studies. Fifty Labor and Delivery practitioners completed examinations using standard methods and then the device. Standard methods yielded an accuracy of 46%. With the device, accuracy increased to 96%, representing an 108% increase. The device was equally accurate regardless of years of experience or level of training. Standard methods resulted in a 10.5% rate of errors of two or greater centimeters from the true value. The device eliminated readings that were incorrect by more than one centimeter.

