Photograph Review. The Sponsor will train an independent reviewer to read DilaCheck® measurements. The reviewer will be provided the photographs taken of DilaCheck® measurements. The reviewer will report two measurements for each photograph. The first will be his/her reading of the exact DilaCheck® measurement, which may be a fraction. The second reading will be his/her reading of the DilaCheck® measurement rounded to the nearest integer; i.e. the second response can only be an integer, not a fraction.

Continuous Feedback. After any individual provider completes five examinations with DilaCheck®, the provider will be provided feedback about whether his/her DilaCheck® measurement readings match those of the independent reviewer.

Power Calculation. The planned enrollment in the study is 50 patients. The following assumptions were used for the power calculations. The agreement in the Control Group was projected to be 49%,⁴ and the agreement in the Device Group was projected to be 90%, based on the results of the simulator trial. The standard deviation was projected to be 23, also based on the standard deviation in the prior simulator trial. With a two-tailed test with $\alpha=0.05$, a sample size of five yields 80% power. However, a trial with five participants will not yield the desired robustness in evaluation of a novel medical device. Instead, a sample size of 25 subjects in each group is planned to allow for examinations across a wide range of patients and providers. A sample size of 50 yields a power of 100% to detect a difference between the two methods given the above assumptions.

Statistical Analysis. The statistical analysis will use a two-tailed level of significance of 0.05. Using SPSS, the proportion of examinations in each group for which the two providers' examinations differed will be determined. A Students T test will be performed to determine whether this difference is significant. The number of examinations for which providers' answers differed by one centimeter and by two or more centimeters for each group will be determined. A Students T test will be performed to determine if the frequency of variation of one centimeter significantly differed between groups. A Students T test will be performed to determine if the frequency of variation of two or more centimeters significantly differed between groups. These analyses will be completed for both the fractional and integral (non-fractional) sets of DilaCheck® measurement readings.

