For participants in the DilaCheck® arm, the subjective and DilaCheck®

DilaCheck® Trial

measurements will be plotted along an X-Y axis and the Pearson correlation coefficient between the two data sets will be calculated. This analysis will be completed for both the fractional and integral (non-fractional) sets of DilaCheck® measurement readings.

The photographs of the DilaCheck® measurements will be read by an independent, blinded reviewer to report the DilaCheck® measurements. The provider's and reviewer's DilaCheck® measurements will be plotted along an X-Y axis and the Pearson correlation coefficient between the two data sets will be calculated. This analysis will be completed for the fractional and integral (non-fractional) sets of DilaCheck® measurement readings.

The correlation between the providers' subjective and DilaCheck® measurements will be analyzed over time. To do so, for providers who complete at least 10 exams, the correlation of the two measurements in the provider's first half of examinations will be compared to the providers' second half of measurements. A T-test will be completed to determine whether the two correlations differ significantly. The analysis will be repeated for both the fractional and integral (non-fractional) sets of DilaCheck® measurement readings and using the data sets of readings from the independent reviewer.

The average pain score in each group will be calculated, and a Students T test will be performed to determine whether pain scores differed significantly between groups. Using logistic regression whether provider number, patient age, gestational age, weight, or epidural status significantly impacted likelihood of agreement or pain score within each group will be determined. The average provider confidence in accuracy will be calculated, and a Students T test will compare if patients' confidence differs significantly between groups. Logistic regression will be used to determine if provider experience or training significantly predicted likelihood of agreement.

Any additional statistical analysis appropriate for the data collected will be performed. For the qualitative data, including descriptions of adverse events and feedback, each of the responses will be reviewed individually. Any serious adverse events will be reported. Any informative feedback or themes in the feedback will also be collated.

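### The regression of agreement on provider experience or training names no term for randomized arm and is not said to be fitted within each group; arm should be in the model

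*Combined protocol and SAP*

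**What the plan says.** All of this is in the combined protocol and SAP, mostly under Statistical Analysis.

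- The model at issue: "Logistic regression will be used to determine if provider experience or training significantly predicted likelihood of agreement". No arm term, interaction or stratification by arm is given.
- Shortly before it, logistic regressions on a list of factors are tied to the arms: whether "weight, or epidural status significantly impacted likelihood of agreement or pain score within each group will be determined". That list opens with provider number and patient age, so one provider-level predictor is already handled by arm.
- Power Calculation gives the expected arm difference: "The agreement in the Control Group was projected to be 49"% and "the agreement in the Device Group was projected to be 90"%. It also says "a sample size of 25 subjects in each group is planned to allow for examinations across a wide range of patients and providers".
- The Protocol Summary reports from the simulator trial: "The device was equally accurate regardless of years of experience or level of training".
- Under Randomization and Data Collection, patients are randomized and the coordinator then calls on two trained providers. No balancing of examiner experience between arms is described. Under Bias, providers are not blinded to arm.
- The Provider Survey collects years of experience and role, so the data for the model will exist.

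**The concern.** An analyst who follows the sentence as written would regress agreement on experience over all 50 pairs. The plan's own projections make arm a very strong predictor: the odds ratio is (0.90/0.10)/(0.49/0.51) = 9.4. Leaving out such a predictor has two consequences.

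First, even with experience perfectly balanced, a logistic model without arm pulls the experience odds ratio toward 1 and loses power. If experience matters for one method and not the other, the single coefficient describes neither.

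Second, randomization balances patients between arms, not examiners. If experienced pairs happen to fall more often in one arm, part of the arm effect is reported as an experience effect, or cancels a real one.

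At stake is what the trial report can say about experience. The primary comparison of agreement between arms does not use this model.

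**Working it through.** **The plan's own figure.** The plan gives no figure for this regression. The nearest is the primary power calculation. With a difference of 41 points and SD 23, n = 2 × [23 × (1.960 + 0.842)/41]² = 4.94, rounded to 5 per arm, which matches the plan. That figure says nothing about the experience model.

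**Inputs from the documents.** 25 pairs per arm, 49% and 90% agreement, two-sided 0.05.

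**Assumptions, not in the documents.** Experience is a binary pair-level label, half of the 50 pairs are experienced, pairs are independent, and a likelihood-ratio test is used. Rejection rates without arm come from exact enumeration, except those in step 1, which are simulated with experience balanced on average. Rates with arm are simulated.

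**1. Balanced experience, common odds ratio of 4.** Keeping the arm averages at 49% and 90% gives 32.3% vs 65.7% agreement in control and 84.4% vs 95.6% with the device (inexperienced vs experienced).
- Pooled experienced: (65.7 + 95.6)/2 = 80.6%. Pooled inexperienced: (32.3 + 84.4)/2 = 58.4%.
- Pooled odds ratio: (0.806/0.194)/(0.584/0.416) = 2.97 instead of 4.
- Simulated power: 40% without arm, 49% with it.

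**2. Effect in finger examinations only.** Control 30% vs 68%, device 90% at both levels.
- True odds ratios: (0.68/0.32)/(0.30/0.70) = 5.0 in control and 1.0 with the device.
- Pooled: (0.79/0.21)/(0.60/0.40) = 2.5, which describes neither method.
- Detection without arm: 25% with 12 experienced pairs in device and 13 in control, and 34% with 13 and 12. With arm: about 40% in both.
- An arm term alone does not separate the two effects. With an odds ratio of 4 in control and 1 with the device, the pooled value is 2.23 and the median arm-adjusted value about 3.0. Agreement has to be shown by arm.

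**3. No experience effect, unbalanced experience.** With k experienced pairs in device and 25 − k in control, expected agreement is [0.90k + 0.49(25 − k)]/25 for experienced pairs and [0.90(25 − k) + 0.49k]/25 for the others.

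| Experienced pairs, device vs control | Agreement, experienced vs not | Apparent odds ratio | False positives without arm | With arm |
|---|---|---|---|---|
| 16 vs 9 | 75.2% vs 63.8% | 1.73 | 12% | 5–6% |
| 17 vs 8 | 76.9% vs 62.1% | 2.03 | 19% | 5–6% |

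**4. How often such gaps arise.** If pairing is random, the number of experienced pairs in one arm is hypergeometric (25 experienced among 50, 25 drawn). A gap of 7 or more in either direction has probability 9%, and 9 or more 2.3%. In the other 91% of trials the rejection rate without arm is about 3 to 8%. Averaged over random pairing it is near 5%.

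**The case against.** The best defence is that the sentence is silent rather than wrong. It does not say that the arms are pooled, and it closes a paragraph in which the other analyses are by group or between groups. A careful analyst might fit it by arm. This stands as to wording: the defect is an unspecified model whose natural reading is pooled. It does not remove the point, because nothing else in the documents supplies an arm term. The general allowance for additional appropriate analyses is not a specification.

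A second defence is that serious confounding needs an imbalance that chance rarely produces. This also stands. A reader might infer that false experience effects are to be expected routinely. A 19 vs 6 split would give about 37% false positives, but a gap of 13 or more has probability about 0.05% under random pairing. Nothing in the documents suggests that examiners are chosen by experience according to arm. The loss of power and the averaging in steps 1 and 2 do not depend on such gaps.

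A reader might also infer that the plan sets out to show that the device works regardless of experience and cannot do so with this model. The documents do not support that. The statement about experience is background on accuracy in the simulator trial. The secondary outcomes listed in the Protocol Summary include none on experience, and no section commits this trial to the claim.

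**Conclusion.** The concern holds in a limited form. The experience/training regression names no arm term and is not said to be within group. Read naturally, it omits a predictor with a projected odds ratio of about 9. The dependable cost is attenuation and lost power: an odds ratio of 4 reads as about 3, and detection of a finger-only effect falls from 40% to between 25 and 34%. The conditional cost is confounding, with false-positive rates of 12% and 19% at gaps of 7 and 9 pairs, reached or exceeded in about 9% and 2% of randomly paired trials. The overall error rate is not inflated.

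These sizes rest on the assumed half-and-half binary split and on the plan's 49% and 90%, so they show the mechanism and are not forecasts. The analysis is secondary and exploratory, and the primary result is untouched. The change is still worth making because it costs almost nothing.

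**What to change.** Replace the sentence with wording such as: Agreement will be modelled on all evaluable pairs by logistic regression with randomized arm and pair-level provider experience (or training) in the same model. The pair-level value will be [the mean, or the lower, of the two examiners' values]. Agreement by experience level will be tabulated separately for each arm.

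The pair-level rule has to be chosen in advance, because each agreement outcome belongs to two examiners and the plan does not say how two values become one.

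If an arm-by-experience interaction is reported, label it exploratory and use an exact or Firth-penalized method. At 90% agreement only 25 × 0.10 = 2.5 disagreements are expected in the device arm. With a 12/13 split, the chance that at least one device-arm cell has none is 0.9¹² + 0.9¹³ − 0.9²⁵ = 0.282 + 0.254 − 0.072 = 46%. Ordinary logistic regression then gives an infinite estimate and no usable interval.

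Cost: one extra model term, one rule and a small table, with no new data. The arm-specific estimates will be imprecise, and the report should say so.

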The proposed study tests the novel DilaCheck® device *in vivo*. The target population is women presenting to the hospital for evaluation of labor or admitted to the Labor and Delivery unit for management of the first stage of labor. The Sponsor (Elm Tree Medical Inc.) trains providers working on the Labor and Delivery unit in the use of DilaCheck®. After informed consent, each patient participant is randomized to receive either two cervical dilation examinations with standard methods or two cervical dilation examinations using the device. Two practitioners complete the cervical examinations separately. The primary outcome is inter-examiner agreement between the control and device arms. Secondary outcomes include agreement of subjective measurements with DilaCheck® measurements over time, agreement of providers' device readings with a blinded reviewer's, patient and provider satisfaction, and documentation of adverse events. Planned enrollment is 50 participants over one year. We hypothesize that the device will increase agreement between the two practitioners from about 49% to 90%, as demonstrated in the simulator trial. The long-term objective is to validate DilaCheck® for use in increasing precision in cervical dilation measurements so that this tool may be available to Labor and Delivery providers to enhance quality of care for pregnant mothers. Increased precision in cervical dilation measurements will enable providers

to make better recommendations for admission to the hospital, augmentation or induction of labor, and cesarean section.

The proposed study is a randomized, controlled trial comparing inter-examiner agreement of standard methods for measuring cervical dilation to a novel medical device. The research population is pregnant women in the first stage of labor.

TRIAL PROTOCOL

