The first provider will dispose of the gloves and device. The first provider will then leave the hospital room. S/he will not speak to the second provider.

The second provider will enter the hospital room. The second provider will introduce him/herself to the patient and explain that s/he is going to perform a cervical examination. The trial coordinator will record the time of the second exam. The second exam must be completed within 10 minutes of the first exam. The second provider will complete a cervical examination as above using a DilaCheck® device. The second provider and trial coordinator will repeat the same steps as described above for the first provider. The second provider will leave the room.

Patient Survey. The trial coordinator will then ask the patient to answer the questions on the Patient Survey. The survey will elicit relevant biological and demographic variables including age, race, ethnicity, gestational age, weight, and use of epidural anesthesia. It will assess the patient's discomfort with the examinations, confidence in the accuracy of the measurements, and satisfaction with the examinations. Patients will be asked to report any side effects they experienced and to provide any comments they have.

Patient Reimbursement. The trial coordinator will offer the patient a \$25 gift certificate to thank her for participating. The patient will sign a receipt to confirm that she received the gift certificate.

Provider Survey. At the end of the trial, the trial coordinator will ask all participating providers to complete the Provider Survey. The survey will elicit the provider's years of experience, role on Labor and Delivery, opinions about inter-examiner agreement using standard methods and using DilaCheck®, and ease of use and satisfaction with the device. The survey will ask whether providers experienced any adverse events and if their patients experienced any adverse events during the trial. They will have the option to provide comments.

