Risks Related to the Study Device. To protect patients against any risk from exposure to the device, the devices will be manufactured under Design Controls and Good Manufacturing Practices, and documentation of biocompatibility and sterility testing of all components can be made available prior to their use. The device was designed to maximize safety and comfort with all soft, medical grade components. The manufacturer tests the devices for reliability. If the device fails in any way, both the trial coordinator and the provider will confirm that all components have been removed fully from the patient. To minimize risk from using a previously untested device, the results of the examinations will not be used in patients' clinical care.

Discomfort. Patients will be reminded that they may withdraw from the study at any time, including after the first examination if they found it too uncomfortable to consent to a second examination. Providers will minimize discomfort through standard techniques such as confirming that the patient would like to continue the procedure before and during an examination. Most women receive epidurals in labor and are thus unlikely to have pain with examinations.

Increased Risk of Infection. The connection between cervical examinations and infection is controversial. Theoretically, insertion of anything into the vagina, even a sterile gloved finger, could introduce bacteria and cause maternal fever and chorioamnionitis. However, recent research has failed to support this theory. For instance, a 2012 trial of 2,395 women revealed no association between number of cervical examinations and intrapartum maternal fever.⁶ Therefore, an additional examination confers at most minimal additional risk of infection to the patient. The device is sterilized using gamma radiation, and we will complete confirmatory testing of sterilization methods prior to shipping the device from the manufacturer.

Unintentional Amniotomy. Unintentional amniotomy is equally likely with the

device and with standard methods since the device has all soft components. If amniotomy is planned, it will be carried out following the two examinations in order to reduce the theoretical risk of infection with examinations following rupture of membranes.

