Inconvenience. Providers will not pressure patients into participating and will clearly inform them that participation is entirely optional and will have no effect on care. The trial will be carried out in an efficient manner with attention paid to minimizing use of the providers' and patients' time.

Risks to Providers. If the Labor and Delivery unit is too busy, providers may opt out of participation for that shift. The study will monitor for any adverse events experienced by the provider through the survey given to all providers at the end of a trial session.

Protection of Vulnerable Populations. This trial meets all conditions as listed in 45 CFR part 46 Subpart B. A simulator trial was conducted as a preclinical study to provide data prior to testing the device with pregnant women. Documentation of sterility and biocompatibility testing of the device materials *in vitro* can be made available prior to use in the trial. There is minimal risk to the fetus, and these risks have been minimized as much as possible for achieving the objectives of the research. The device holds the prospect of direct benefit to both pregnant women and fetuses. The purpose of the research is the development of important biomedical knowledge: determination of the efficacy and safety of this novel device that cannot be obtained by other means. Researchers will obtain consent from every patient in accordance with the informed consent provisions of 45 CFR 46 Subpart A. No pregnancies will be terminated. There is no contact with neonates.

Potential Benefits of the Proposed Research to Human Subjects and Others.

Human subjects will benefit from participating in the research through their receipt of education on cervical dilation examinations via the consent process and through the knowledge that they have contributed to the care of future laboring women. Providers will benefit from participation through receiving individualized training in the use of the device, through gaining experience in clinical trials, and through the option to participate in editing the scholarly journal article in exchange for authorship. Because patients are exposed to a non-significant level of risk by participating in the study, the benefits to them, to providers, and to the field of obstetrics and future laboring mothers outweighs the risks.

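### Adverse events are a secondary outcome, but no summary by randomized arm is planned, and the provider question states no link to a subject or examination

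*Combined protocol and SAP*

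**What the plan says.** The Protocol Summary ends its list of secondary outcomes with "patient and provider satisfaction, and documentation of adverse events". Protection of Vulnerable Populations gives as a purpose of the research the "determination of the efficacy and safety of this novel device".

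Statistical Analysis has one provision for these data, which it classes as qualitative: "including descriptions of adverse events and feedback, each of the responses will be reviewed individually. Any serious adverse events will be reported". It gives no count, denominator, split by arm or interval. The same section does plan between-group tests of pain score and of patients' confidence in the measurements.

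Events reach the trial by two surveys. Under Patient Survey, after the examinations, "Patients will be asked to report any side effects they experienced and to provide any comments they have". Under Provider Survey, which is placed once at the close of the trial, "The survey will ask whether providers experienced any adverse events and if their patients experienced any adverse events during the trial". Risks to Providers instead refers to a provider survey after each trial session, in a sentence about events that the providers themselves experience.

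On risk, Study Device Specifications and Potential Risks of Study Participation say that no risk beyond a standard gloved examination is anticipated. Unintentional Amniotomy is unqualified: "Unintentional amniotomy is equally likely with the" device as with standard methods.

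**The concern.** The trial has a randomized control arm, a named safety outcome and a named device-relevant event, accidental rupture of membranes. Eligibility requires intact membranes, so every woman enters at risk of that event. Yet nothing in the analysis plan counts it, or any other adverse event, by arm.

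The provider question adds a data problem. Randomization is by woman, each woman has two examiners, and nothing confines a provider to one arm. A provider asked once about all of his or her patients gives a pooled answer. As described, that answer need not identify the woman, the examination or the arm, and two providers may describe the same event.

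The safety outcome could then be reported as a narrative from which no rate can be recovered, and the statement of equal amniotomy risk would stand with no trial figure beside it. The primary outcome is not affected.

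**Working it through.** **1. Is there a figure to reproduce?** No. The plan gives no adverse event rate, safety margin or safety power. The figures under Power Calculation concern examiner agreement only. The one input taken from there is 25 women per arm.

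**2. What each provision supplies.**

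| Section | What it yields | Link to arm | By-arm summary specified |
|---|---|---|---|
| Patient Survey, side effects | Report from each woman after her examinations | Yes: pain is also collected from patients and is compared by group | No |
| Statistical Analysis, pain | Pain score | Yes | Yes, t test |
| Provider Survey | Answer about a provider's patients together | None stated | No |
| Statistical Analysis, event descriptions | Reading one by one | Not stated | No |
| TJU IRB Review | Adverse events, withdrawals, complaints | Not stated | No |
| DSMB Review | Monthly listing of all adverse events | Not stated | No |
| ClinicalTrials.gov | Adverse events in the results summary | Not stated | No |

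Only pain has a planned comparison. Patient-reported side effects could be compared, but no comparison is planned. Provider-reported patient events have no stated link that would allow one.

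**3. Double counting.** There are two examinations per woman, so 50 × 2 = 100 examinations, each woman seen by two providers. Suppose one device-arm rupture is reported by both of her examiners and tabulated as two women:
- counted once: 1/25 = 4%, exact 95% CI 0.1% to 20.4%;
- counted twice: 2/25 = 8%, exact 95% CI 1.0% to 26.0%.

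**4. What a by-arm table could show at 25 per arm.**
- No events in one arm: the exact two-sided 95% upper limit is 1 − 0.025^(1/25) = 13.7%. The one-sided limit is 1 − 0.05^(1/25) = 11.3%.
- No events in either arm: the Wilson upper limit for 0/25 is z²/(n + z²) = 3.84/28.84 = 13.3%, so the Newcombe 95% interval for the difference is −13.3 to +13.3 points. For 1/25 against 1/25 it is about ±15.9 points.
- Fisher's exact test, two-sided: 5/25 against 0/25 gives 2 × C(25,5)/C(50,5) = 2 × 53,130/2,118,760 = 0.0502. For 6/25 against 0/25, 2 × 177,100/15,890,700 = 0.022.
- Fisher power under assumed rates (the documents give none): 7% for 5% against 15%, 20% for 5% against 20%, 82% for 5% against 40%.
- Chance of at least one event among 25 women, 1 − (1 − p)^25: 22% at an assumed true risk of 1%, 64% at 4%, 93% at 10%.

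The widths in step 4 come from the sample size and would be the same after the fix. They do not measure the flaw. They show why the table must be labelled descriptive, and why no events, or similar counts in the two arms, would not establish equal risk.

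**The case against.** The strongest reply is that the safety data are broader than the Statistical Analysis section suggests, and much of that reply stands. It rules out several stronger readings that a reader might infer.

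- *Only serious events will be reported.* Not supported. Statistical Analysis promises to report serious events but does not say that others are withheld. TJU IRB Review, DSMB Review and ClinicalTrials.gov cover adverse events generally.
- *No event can be tied to an arm.* Not supported. Each woman reports her own side effects and has a Subject Number and a randomized arm.
- *Discomfort is not compared.* Not supported. Pain scores are tested between groups. Surveys from women who lack a reading are kept because they may explain why, and withdrawals go to the IRB. What is missing is a by-arm count of women who stop after the first examination.
- *Providers cannot identify the woman.* Too strong. The form is not in the documents; its description merely states no link. If the survey is given after each session, as Risks to Providers implies, pooling is much reduced. The two timings conflict.
- *The plan claims that the device adds no risk.* Too strong. Elsewhere added risk is only not anticipated. The amniotomy sentence is unqualified, but it is a risk rationale in the human-subjects section, not a planned trial conclusion.

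It can also be said that the plan allows any further suitable analysis, and that a comparison of 25 with 25 has little power. The first point permits a table but commits to none. The second is a reason to show intervals, not to omit counts.

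**Conclusion.** The point holds in a limited form. A named secondary outcome has no prespecified by-arm summary, and provider-reported patient events, as described, may be neither attributable to an arm nor free of duplication. The provisions for the IRB, the DSMB and the registry ensure that events are passed on, but none specifies the summary.

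The effect is on the safety statement alone. One duplicated report would double an arm's rate from 4% to 8%. With no summary and interval, a reader would not see that no events in 25 women is compatible with a true risk of up to 13.7%.

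This rests on 25 women per arm all having at least one study examination, and on the provider form carrying no more than its description states. If the form already records Subject Number and examination, the attribution problem falls away and the missing by-arm summary remains. It is a cheap improvement worth making, not a threat to the trial's main result.

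**What to change.** 1. In Statistical Analysis, add to the individual reading a table of all adverse events and side effects, serious or not, by randomized arm. Count women with at least one event over women with at least one study examination. Give exact 95% confidence intervals for each arm and the between-arm difference with its interval, and label the table descriptive.
2. Include separate rows for unintentional rupture of membranes and for stopping after the first examination.
3. Add no fever or infection row unless those data are already recorded. Sources of Research Material lists neither, and the Patient Survey directly follows the examinations, so filling the row would need new data collection.
4. Have provider-reported patient events entered against Subject Number and examination (first or second), and count each event once when both examiners, or the woman and an examiner, report it.
5. Reconcile the timing of the provider survey between Provider Survey and Risks to Providers.
6. Reword the amniotomy statement as an expectation that the trial will describe, not establish.

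The cost is one table, two form fields and some wording, with no extra patients. The downside for the sponsor is a safety statement that reads less favourably because the intervals are wide.
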